The project seeks to put people at the center of interventions while respecting their digital rights. The comparison between 360V, VR, RA, web-based information, written information and standard procedure, to determine which is the best way to train home caregivers in order to increase their technical competences and soft skills, including self-confidence, is the outcome this project would analyze. This study aims to explore the

experience and needs of caregivers (skilled and unskilled) of dependent and chronically ill patients and then to design and test the effectiveness of several interventions aimed at promoting safer medication use in the home.

Methods

Intervention design

This is a prospective, parallel, fully randomized (with simple random assignment of participants to one of six arms) experimental study to compare (inter-group and intra-subject PRE and POST measures) educational interventions aimed at training caregivers using typical scenarios during their work at home in order to reduce medication and caring errors and improve caregivers' motivations and self-efficacy.

Present protocol underwent the revision and approval of an Ethics Committee Board, obtaining the approval in December 2021 and January 2023 (CODES 21/063; 22/079 and 22/080). ClinicalTrial xxxxxxxx

Recruitment

Recruitment will be carried out in the collaborating centers through the programmes for complex chronic patients, schools for carers, and associations and foundations for carers and/or diseases causing dependency situations using the "snowball" technique.

Participants (caregivers) will be recruited during a regular consultation where they go to accompany the person they care for to the consultation, or in a clinical consultation of their own where they can comment that they are caring for a person at home. Recruitment will be carried out through systematic sampling according to the list of people seen in the consultation, using $k=3$. The collaborator will systematically select 1 out of every 3 patients cited in the consultation list. If the person refuses to be included in the study, the next person on the list will be invited and then $k=3$ will be applied.

Additionally, in the recruitment of caregivers, two aspects must be considered:

- Qualification of the caregivers

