- Carers with problems of vertigo, tinnitus, motion sickness, epilepsy, seizures or similar symptoms, severe cardiac conditions or wearing a cardiac pacemaker or hearing aid.

Inclusion criteria for professionals

- Professionals with at least 5 years of experience working in hospitals, health centers and day-care centers.

Intervention design

Medication errors refer to any avoidable incident that may cause inappropriate use of medication, or harm to the patient, while the drug is under the control of the healthcare professional, patient, or caregivers. Care errors to describe any avoidable incident during care, grooming, mobilization that can cause or does cause harm to the patient and that, in our case, occurs in the home and is performed by caregivers.

Care can come from qualified or mostly unqualified people (family members or untrained carers) who take on complex tasks with little training. In this project we consider the limit of 20 hours of training to differentiate between qualified and unqualified carers.

The study includes two phases, a first phase of data collection and a second experimental phase. Some of the centers may not participate in one of these arms due to their idiosyncrasies. The same applies to the day-to-day situations listed in the document.

Phase 1. In this phase, already completed, information on knowledge, needs and differences in responsibility for the safe use of medication and dispensing of care among caregivers has been captured through nominal groups and an online survey disseminated via email to caregiver associations, which has allowed for the identification of errors, causes and consequences and risk factors that favor these errors. This information feeds into the design of situations for the experimental phase.

[figure not shown]
Phase 2. A true experimental design will be conducted to determine the effectiveness of different interventions, each of them reflected in an arm, to reduce errors during the care and administration of medication at home by caregivers.

To be able to determine which educational solutions are optimal, the study has the following arms:

- *Arm 1-Control group:* Natural intervention (actual provision of information and answering of questions). **This arm will evaluate the natural learning during the action.**

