- *Arm 2-Experimental group 2:* Intervention with written materials and demonstration videos specifically designed for this study. **This arm will evaluate the effect of a traditional, more passive form of learning, with little degree of interaction with the content.**
- *Arm 3-Experimental group 3:* Psychoeducational intervention specifically designed for this study. **With this specific intervention, participants will learn by sharing information with the session facilitator and other participants, which will facilitate a more active form of learning, with a higher degree of interaction than the previous arm.**
- *Arm 4-Experimental group 4:* Intervention using immersion 360 degrees specifically designed for this study. **Participants enrolled in this arm, by completing it, is assumed that will experience a form of learning more participatory and immersive than conventional videos, as they can interact with the content by changing the camera angle.**
- *Arm 5-Experimental group 5:* Virtual Reality intervention specifically designed for this study. **Using VR to learn procedures will encourage caregivers to learn in a fully immersive and participatory environment where they will have to interact with the virtual content, enhancing their learning experience.**
- *Arm 6-Experimental group 6:* Augmented Reality Intervention specifically designed for this study. **This intervention will increase participants' skills through active learning as they interact with real-world care situations while receiving simultaneous support from AR devices.**

In each of the experimental groups, key patient care situations will be developed and the educational solutions for each of the arms will be adapted.

The process of this phase of the study is summarized in the following **figure**.

The evaluation of the effectiveness of each of the arms will be measured, among other ways, by recording two attempts to execute the care situation to be trained in the intervention. This recording will be made at three different times: at the baseline visit (pre-intervention), after the intervention (post-intervention) and 6 months after the end of the intervention (follow-up). The control group is an exception, as there is no specific intervention and therefore the post-intervention recording is omitted. Thus, in the case of the control group, only the pre-intervention and 6 months after the intervention will be recorded.

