Time of use will be recorded and correlation analyses will be performed to determine the size and direction of the effect on the outcomes. The difference between the measures considered above rated will be considered before and after (PRE and POST intervention (time 0) and FOLLOW UP (+6 months)) the experimental intervention sessions as outcome variables. The distribution of the data will be tested using the Kolmogorov-Smirnov test, the measures will be compared with an ANOVA test for normally distributed continuous variables, and the Kruskal-Wallis test if the distribution is not normal. Given the number of time-ordered and repeated variables per subject, they will be explored using a linear mixed effects model (LMM). Data will be stratified taking into account gender, age, recipient profile and time of use. P values <0.05 are considered to indicate statistically significant differences. Statistical analyses will be performed on R and SPSS. If the intervention is successful, the control group will be invited to receive the treatment of the experimental group on the same terms. The results of this project will be prepared for dissemination according to the contents of the "Standards for reporting qualitative research" (SRQR) guidelines for qualitative studies, the Consort checklist for randomized trials, and the CHEERS checklist for economic outcome evaluations.

Discussion sobre utilidad o lo que hacen otros estudios

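### Arms are compared on before-after differences; adjusting the +6-month score for the PRE score already collected is more precise at no cost in data, and the contrasts between solutions should be named in advance

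*Combined protocol and SAP*

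**What the plan says.** All the analysis text is in the Data analysis section.

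- **Outcome scale:** "The difference between the measures considered above rated will be considered before and after" the sessions, with PRE, POST and +6 months listed together.
- **Between-arm test:** after a Kolmogorov-Smirnov check, "the measures will be compared with an ANOVA test for normally distributed continuous variables, and the Kruskal-Wallis test if the distribution is not normal".
- **Repeated measures:** "they will be explored using a linear mixed effects model (LMM". No fixed effects, random effects or covariance structure follow. The next sentence lists stratification by gender, age, recipient profile and time of use; the PRE score is not in that list.
- **Threshold:** "P values <0.05 are considered to indicate statistically significant differences". No pairwise step, contrast with control or multiplicity rule is stated or excluded.

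Three other statements bear on this.

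- **Aim:** Overview and aim sets out "to determine which is the best way to train home caregivers". The Abstract and the second Intervention design section likewise seek the optimal solution.
- **Measurement:** under Phase 2, effectiveness is "measured, among other ways, by recording two attempts" at PRE, POST and +6 months. "The control group is an exception, as there is no specific intervention and therefore the post-intervention recording is omitted". The Post-intervention visit section adds that control completes no POST notebook either.
- **Centres:** "Some of the centers may not participate in one of these arms due to their idiosyncrasies".

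**The concern.** The PRE score is collected in all six arms. Subtracting it from the later score uses it with a fixed weight of 1. Regressing the later score on it uses the best-fitting weight, which gives a tighter estimate of the arm effect whenever the PRE-outcome correlation is below 1. The plan as written may leave that precision unused.

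The mixed model does not settle the matter, because its terms decide whether it behaves like a change-score analysis or a PRE-adjusted one. Nor does the section separate the two time points: POST can compare only arms 2 to 6, and all six arms can be compared only at +6 months.

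A secondary concern is that a six-arm omnibus test can show that some arm differs, but not which solution is better than which. Yet the aims ask for the best one. How to get from one to the other is left open until the data are in hand.

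**Working it through.** **Inputs.** From the documents: 420 participants, six arms, simple randomisation, threshold 0.05, PRE recorded in all arms, no POST in control. The documents give no effect size, SD, power, dropout or correlation, so 420 can be neither reproduced nor called wrong.

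**Assumptions.** 420/6 = 70 per arm analysed, complete data, normal scores, equal SD (set to 1) at both times, two-sided tests, rho from 0.3 to 0.9, effects in raw-score SDs. Simple randomisation would give roughly 55 to 85 in any one arm (95% range), so 70 is an average.

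**1. Variance of the two approaches.** Change score: 2(1 − rho). PRE-adjusted: 1 − rho², ignoring the trivial cost of estimating one slope. Ratio: 2(1 − rho)/[(1 − rho)(1 + rho)] = 2/(1 + rho).

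| rho | Change | PRE-adjusted | Ratio |
|---|---|---|---|
| 0.3 | 1.40 | 0.91 | 1.54 |
| 0.5 | 1.00 | 0.75 | 1.33 |
| 0.7 | 0.60 | 0.51 | 1.18 |
| 0.9 | 0.20 | 0.19 | 1.05 |

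**2. What the mixed model would do.** Generalised least squares with the control-by-POST cell missing and compound symmetry gives the variance of the +6-month contrast. With PRE means free in each arm, its ratio to the PRE-adjusted variance is 1.54/1.33/1.18/1.05, exactly that of the change score. With one common PRE mean, the ratio is 1.00 at every rho.

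**3. Power for one pair of arms.** Noncentral t with noncentrality d/[SD × √(2/70)] and critical value 1.97. Example, d = 0.5 and rho = 0.5: change score 0.5/(1.000 × 0.169) = 2.96, power 84%; PRE-adjusted 0.5/(0.866 × 0.169) = 3.42, power 93%.

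| Difference | Analysis | rho 0.3 | rho 0.5 | rho 0.7 |
|---|---|---|---|---|
| 0.5 SD | Change score | 70% | 84% | 97% |
| 0.5 SD | PRE-adjusted | 87% | 93% | 98% |
| 0.3 SD | Change score | 32% | 43% | 63% |
| 0.3 SD | PRE-adjusted | 46% | 53% | 70% |

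At rho 0.9 and 0.3 SD, power goes from 97.7% to 98.2%.

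**4. Price of controlling the contrasts (PRE-adjusted).** Critical |t| is about 2.52 for Dunnett (five comparisons with control) and 2.86 for Tukey (15 pairs).

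| Difference | Family | rho 0.3 | rho 0.5 | rho 0.7 |
|---|---|---|---|---|
| 0.5 SD | Dunnett | 72% | 81% | 95% |
| 0.5 SD | Tukey | 59% | 71% | 90% |
| 0.3 SD | Dunnett | 26% | 32% | 49% |
| 0.3 SD | Tukey | 16% | 21% | 35% |

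**5. If a significant omnibus test on change scores were followed by unadjusted pairs** (a step the plan does not state). Simulation with five equal solutions and control 0.3 SD worse: some pair of solutions is falsely separated in about 15/18/23/28% of trials at rho 0.3/0.5/0.7/0.9, against about 3.5% with Tukey. One solution falsely beats all four others in about 0.4%. If no arm differs, the omnibus gate keeps the error below 5%.

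**6. Centre.** In a balanced layout of six arms with k arms per centre and no centre effect (assumptions), centre adjustment has efficiency 6(k − 1)/(5k): 24/25 = 0.96 for k = 5 and 12/15 = 0.80 for k = 3. At 0.80 and 0.3 SD, moving from an unadjusted change score to PRE plus centre takes power from 63% to 60% at rho 0.7 and from 98% to 95% at rho 0.9. It still rises at rho 0.3 and 0.5.

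**The case against.** The strongest reply is that nothing here is an error. Change scores are unbiased under randomisation, the gain depends on an undocumented rho, and it is only 5% of variance at rho 0.9. That stands: the point about PRE is an improvement, not a correction of a bias, though it draws only on data already in hand.

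The plan also includes a mixed model, and one containing arm would give arm-specific estimates; reading much into the word for exploring would be unfair. This stands in part. The plan is not confined to the omnibus test, but step 2 shows that the unstated terms decide the precision. The stratification list does not fill the gap: it may describe subgroups rather than covariates, and it omits PRE.

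A reader might infer that the plan carries a 15–28% false-positive rate. The documents do not support that. The figure needs an unadjusted pairwise step that the plan neither states nor excludes, and five exactly equal solutions. For the aim of naming a single best solution, the matching figure is about 0.4%. Whether familywise control over all 15 pairs is worth its loss of power is debatable.

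A reader might also infer that every addition to the model is free. That holds for PRE but not for centre (step 6).

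**Conclusion.** The point holds as an improvement in precision together with a gap in specification. The change-score comparison is valid but has 5% to 54% more variance than the PRE-adjusted one for rho between 0.9 and 0.3. At 0.5 SD this is worth about 17, 9 and 2 points of power at rho 0.3, 0.5 and 0.7, and almost nothing at 0.9. These sizes rest on equal SDs, 70 per arm, complete normal data and an assumed rho. The direction needs only equal SDs and rho below 1.

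Two parts need no assumption: control has no POST measure, so comparisons with control exist only at +6 months; and no contrast procedure is stated for saying which solution is better. The documents do not show that the planned analysis is biased, that 420 is the wrong number, or that the team intends unadjusted pairwise testing.

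**What to change.** **Main change (wording only; no new data, one degree of freedom).**

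- Make the main between-arm analysis a linear model of the +6-month score on arm (six levels) with the PRE score as covariate. Score the two attempts the same way at each visit. An equivalent choice is a mixed model with a common PRE mean and no control-by-POST cell.
- Analyse POST in the same way among arms 2 to 6 only.
- Use this model in place of both the change-score ANOVA and the test-driven switch to Kruskal-Wallis. Add a robust or rank-based sensitivity analysis if residuals are clearly non-normal.
- Say whether gender, age and recipient profile are covariates or subgroups. Keep time of use out of the between-arm model, because it is measured after randomisation.

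**Secondary change (wording, but it costs power).** Name one contrast family at +6 months in advance, for example Dunnett against control or Tukey over all pairs. The choice is the sponsor's. Against 87/93/98% for an unadjusted PRE-adjusted contrast at 0.5 SD (rho 0.3/0.5/0.7), Dunnett gives 72/81/95% and Tukey 59/71/90%.

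**To decide separately.** Centre adjustment may be needed against bias because centres may skip arms, but it can lower power when centres run few arms. The primary outcome, multiplicity across outcomes and the missing-data rule are not settled by this change.

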Title: Innovative Teaching Solutions to Improve the Outcomes of Home Caregivers

V1.01.2023

PI00868

Abstract

Justification. Caring multipathological and polymedicated patients at homes is inexorably growing in OCDE countries, with a greater risk of suffering diverse errors made by their carers. **Objective.** To promote the training of home caregivers using five different educational solutions compared against the natural intervention. **Method.** Prospective, parallel and mixed research study with two phases. *Candidates:* will be home-based caregivers caring either a person with multiple co-morbid conditions or polymedication or a person that have a permanent device implanted such as a Port-a-Cath. *First phase:* Expert groups joined together to design and plan potential educational solutions directed to caregivers based on the identification of medication and home care errors, their causes and consequences and risk factors that favor them. *Second phase:* Inter- and intrasubject single-factor experimental design (6 groups, 5 experimental groups and control, with pre-post- intervention and follow up measures), simple random assignment, to determine the effectiveness several educational solutions (n=420 participants). The study will be carried out in primary care centers and caregivers' associations in Valencian Community, Andalusia, Madrid, Murcia and Catalonia. **Expected results.** To identify critical elements for risk management in the home for caregivers. To find the most effective and optimal educational solution that also reduces the impact of gender bias in this activity.

ClinicalTrial xxxxxxxxx

Overview and aim

The increase in the number of people with chronic diseases is a significant burden of care and consumption of health care resources all over the world. Most are elderly and, in some degree, dependent for their daily activities of a caregiver. Thanks to the work of people caring people at home, these people survive while preserving their well-being as much as possible. This work covers a range of activities from physical and emotional support for the promotion of autonomy to the management of their pharmacological treatment, in many cases applying more complex care. The sex bias generally prompts that the provision of care for dependent persons is carried out by women, which widens the already existing gender gap to the detriment of women.

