- *Arms with intervention at home (Arm 2 - Intervention with written materials and videos, Arm 4 - Intervention with 360° materials and Arm 6 - Intervention with augmented reality):* the intervention is carried out by the caregiver alone at home, so it is useful to hold a training session at the centre to explain to the caregiver the task to be carried out at home.
- *Arms with intervention at the centre (Arm 3 - psychoeducational intervention, Arm 5 - intervention with virtual reality):* the stipulated sessions of each arm will be carried out in the rooms provided in the centres.

Post-intervention visit

Once each arm's own intervention has been received, participants will be called to participate in a new recording of the care work in the medical centre. As in the pre-intervention, at the beginning of the recording, the caregiver's identification code must be shown. At the end, a new link and QR with the Post-intervention Caregiver's Notebook will be shared with them so that they can fill it in online through the link. This flow will be for all arms except for the control arm (Arm 1), where no recording will be carried out and no post-intervention caregiver's notebook will be completed.

Again, the videos resulting from the recordings of this session should be analysed following the available rubric.

Follow-up visit (+6 months)

After 6 months (follow-up phase), participants will be recorded making two attempts at the care they were trained in. As in the previous recordings, at the beginning of the recording, the caregiver's identification code must be shown. At the end, they will be given a new QR and link to the Caregiver's Notebook Follow-up.

Gold Standard (professional group)

In addition to the participants in the control and experimental groups, the study will also include a group of 10 healthcare professionals, who will act as the Gold Standard group. This group will be recorded performing all the care situations to be trained to have a standard measure with which to compare the performance of the caregivers, once they have received the training.

Data analysis

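### The arm comparison names neither care situation nor centre and sets no common score scale: this costs precision, and can bias arms only if arms and situations are linked across centres

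*Combined protocol and SAP*

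**What the plan says.** **Several tasks.** Under Phase 2 of the Intervention design, "key patient care situations will be developed" for the experimental groups. Each carer is filmed making two attempts at the situation to be trained; the singular suggests one situation per carer. Their number is not given, nor is the way a carer comes to be assigned one.

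**Uneven availability.** The same section lets a centre opt out of an arm, then adds: "The same applies to the day-to-day situations listed in the document". The recruitment criteria refer to centre templates tailored to the arms that each centre has taken on. The Methods nevertheless call the trial "fully randomized (with simple random assignment of participants to one of six arms".

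**Scoring.** Recordings are rated with a checklist. Its item count, its scale and any situation-specific versions are not described. Of the ten professionals in the Gold Standard section, the plan says: "This group will be recorded performing all the care situations to be trained". No rule converts carers' scores to that reference.

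**Analysis.** The outcome is a change: "The difference between the measures considered above rated will be considered before and after" the sessions. Then "the measures will be compared with an ANOVA test for normally distributed continuous variables", or Kruskal-Wallis otherwise. A mixed model is added without a list of terms. Stratification uses recipient profile, time of use, age and gender. Situation and centre are absent.

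**The concern.** Carers doing different tasks contribute to one arm comparison, and nothing in it accounts for the task. If typical improvement differs between tasks, that spread goes into the residual and every arm comparison loses precision.

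There is also a possible route to bias. If the centres that drop an arm also tend to drop certain situations, the arms end up with different task mixes, and a difference between tasks can pass for a difference between training methods. The control arm adds to this. Follow-up records the care in which participants were trained, but controls receive no training, so the plan does not define which situation they perform.

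Recipient profile helps only in part: it separates the two patient groups, not the situations within them.

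**Working it through.** **The plan's own figure.** The Abstract gives the size of the trial: "to determine the effectiveness several educational solutions (n=420 participants". No effect size, SD, power or dropout accompanies it, so 420 cannot be reproduced. The only error-rate statement is "P values <0.05 are considered to indicate statistically significant differences".

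**Inputs.**
- From the documents: 420 participants, six arms, level 0.05.
- Assumed: equal arms, 420 / 6 = 70; two-sided testing; true pairwise effect d = 0.5 in within-situation SD; situation share r of change-score variance from 0 to 30%.

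**Step 1. What the change score removes.** Take four situations with constant difficulty offsets of -6, -2, 2 and 6 and an occasion SD of 3.
- Offset variance is (36 + 4 + 4 + 36) / 4 = 20.
- Situation share of the post score is 20 / (20 + 9) = 69%.
- In post minus pre, the offset cancels and the share is about 0%.

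Constant difficulty is therefore already dealt with.

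**Step 2. What it does not remove.** Tasks with different room to improve have different mean changes. Checklist length has the same effect if raw counts are used. Assume a 15-point percentage gain, with SD 15 points, on every task.
- 10 v 20 items: mean gains 1.5 and 3.0 items. Between-task variance is 0.75² = 0.5625, within-task variance is (1.5² + 3.0²) / 2 = 5.625, and the share is 0.5625 / 6.1875 = 9%.
- 10 v 30 items: mean gains 1.5 and 4.5 items. Between-task variance is 1.5² = 2.25, within-task variance is (1.5² + 4.5²) / 2 = 11.25, and the share is 2.25 / 13.5 = 17%.

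These lengths are illustrative; none is documented.

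**Step 3. Precision when every arm has the same task mix.** Without a situation term the SD is inflated by 1/√(1 - r), so

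power = Φ(d·√(1 - r)·√(n/2) - 1.96), with d·√(n/2) = 0.5 × √35 = 2.958.

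| r | Power without term | Power with term | n per arm for 80%, without term |
|---|---|---|---|
| 0 | 84.1% | 84.1% | 63 |
| 10% | 80.1% | 84.1% | 70 |
| 20% | 75.4% | 84.1% | 79 |
| 30% | 69.7% | 84.1% | 90 |

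The last column is 2 × (1.96 + 0.8416)² / 0.25 = 62.8, divided by (1 - r) and rounded up. With the term it stays at 63. The power column ignores the few degrees of freedom used.

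A simulation (3,000 trials per setting, 420 participants, six arms, four situations, one arm shifted by 0.5) gave a similar pattern for the six-arm F test. Without the term, power was 85%, 79%, 75% and 68% at shares of 0, 10%, 20% and 30%. With the term it was 84% to 86% throughout.

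**Step 4. False arm effects, no true effect, same simulation design.**
- Same mix in every arm: type I error without the term was 4.6% to 5.3%. The level holds.
- Two of the six arms lack one of the four situations: 14%, 28% and 41% at shares of 10%, 20% and 30%.
- With a situation term: 4.5% to 5.2% in every setting.

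The second case shows what a linked mix would do. It is not a forecast, because no such link is documented.

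**The case against.** The strongest reply has four parts.

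- **Pooling is inferred.** The Data analysis section does not say whether tests are run by situation, and the mixed model's terms are open. This stands. The finding is that situation is not named anywhere in the analysis, not that the plan declares it will be ignored.
- **Differing checklists are not documented.** The plan speaks of a rubric in the singular, and a percentage score is compatible with the text. This also stands. A reader might infer large power losses from very unequal raw-count checklists, but the documents support no such figure. Part of any such loss would come from the SD growing with list length, which a situation term cannot recover and rescaling can.
- **The change score handles difficulty.** It does so for constant difficulty, but not for unequal room to improve.
- **Randomisation protects the comparison.** A reader might infer that omitting situation biases the arms as a matter of course. It does not: with the same mix in every arm the test keeps its level. Bias needs arm and situation availability to be linked across centres. The plan allows both to vary by centre but does not say that they vary together.

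What remains is that recipient profile is only a coarse proxy for task. The professionals' recordings would supply a reference for each situation, but no rule uses them.

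**Conclusion.** The point holds in a limited form and is worth correcting. The planned comparison names neither care situation nor centre and sets no common scale.

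The expected cost is precision. Under the assumptions of 70 per arm, d = 0.5 and a two-sided 5% level, pairwise power falls from 84% to about 80%, 75% or 70% if situation explains 10%, 20% or 30% of change-score variance. If gains barely differ between situations and the score is already a percentage, the cost is close to nil.

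A false arm effect is conditional on a link between arms and situations across centres. The documents leave that possible but do not establish it, so the plan should not be described as biased on this ground.

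**What to change.** 1. State how care situations are assigned. Fix and record each participant's situation before the arm is known, controls included.
2. Define the outcome as the percentage of checklist items in error, or standardise it within situation. The professionals' recordings can serve as the reference for each situation.
3. Add care situation and centre as factors in the arm comparison and in the mixed model, and list the model terms. Kruskal-Wallis takes no such factors, so the non-normal fallback needs a form that does, such as a rank test stratified by situation.
4. Report a situation-by-arm table, so that any imbalance is visible.

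The cost is analysis-plan wording, one variable to record per participant, and a few degrees of freedom out of 420.
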